## Summary and considerations

Our data constitute the first phosphoproteomic taxonomy of TNBC and constitutes a seminal manuscript in the field recently published in Nature Communications [1].

This tool allows not only to find novel phosphosites and kinases that account for the biology of this disease but also to use this knowledge to accurately classify this disease for the first time. We were also able to build a signature that is sufficiently parsimonious and easy to measure in daily clinical routine samples embedded in paraffin. More importantly, this taxonomy is not only able to provide prognosis information: it also reveals the targets that a patient should have modulated with targeted inhibitors in case her taxonomy results classified her in the adverse prognosis subgroup. Thus, our taxonomy also provides therapeutic solutions.

Next step is to validate the therapeutic results in humans. To this end, it is necessary to assess each of the possible 2-by-2 combinations individually, in advanced TNBC in order to detect which of them yield signals of activity. Although for some of these targets (i.e., PNKP, p70S6K) there are not clinical-grade available compounds, Pfizer has developed agents that effectively inhibit several of the kinases in the list, such as cKIT (sunitinib) or CDK6 (palbociclib, which according to our preclinical data seems the cornerstone agent for the doublets). In addition, a recent partnership with Array Biopharma will allow Pfizer developing the MEK inhibitor binimetinib (effective against models with high ERK signaling output).

Some previous studies have assessed the role of inhibitors against some of the former kinases but that have always been performed in monotherapy, without taking into account that the maintenance of aggressive TNBC biology, according to our results, requires the activity of several of these axes. Thus, it is unlikely to achieve a durable and/or meaningful benefit by using single-agent approaches. These agents have to be evaluated at least in 2-by-2 combinations.

Among all the combinations tested, CDK+MEK/ERK inhibition was the most powerful [1]. In order to set a proof of concept, and prior to launch a multi-arm trial with treatment allocation based on the status of each of the six kinases, we propose to launch a single-arm pilot trial testing palbociclib + binimetinib (CDK4/6 plus MEK inhibition) in advanced TNBC. Only patients within the highest quartiles of activation of CDK4/6 and/or ERK will be candidates for the trial. If no signal of activity is detected in this pilot trial, it is unlikely that the other combinations will be active.

In addition, it would make unlikely as well to observe activity outside the subsets of patients with CDK4/6/ERK within the highest levels of activation. Although this requires real-time determination by a centralized pathology lab during the screening procedures, such biomarker enrichment will allow maximizing the chances of success. Real-time patient selection assumes a positivity of activated ERK, CDK4/6 or both in 42% of incident TNBC patients [1]. Patients candidates for this trial will have sent to CNIO their tumor sample. Two duplicates for each staining will be processed and acquired by an automated Ariol Scanning Machine after pathologic

evaluation. We will set-up a circuit that supports sample shipment/processing twice per week coupled with a response time (with final pathologic evaluation and H-score report communicated to the CRO) of less than 7 days, in order to avoid delays in the screening processes. Should this pilot trial be successful, other doublets may be tested and also different cut-off values might be used for trial selection in the future.

Recent preclinical studies suggest that alternating schedules (continuous palbociclib administration plus 3 weeks on/1 off MEK inhibitor, or continuous MEK inhibitor plus 3 weeks on/1 off palbociclib) are more effective and better tolerated in animals than continuous dosing of both agents alone [41]. We propose to use as starting dose that one found as RP2D in a similar study ongoing in lung cancer that has already completed the safety lead-in part (NCT03170206, data on file). In this study binimatinib 45 mg BID was the recommended phase II dose [42]. Another study with binimatinib and palbociclib in colorectal cancer (NCT03981614) uses the same starting doses of both drugs without a preceding dose-escalation phase. A subsequent study in a larger number of patients in advanced melanoma showed that a significant number (61%) of patients had to undergo dose reduction to 30 mg/BID because of the former side effects and others such as hypertension, decreased LVEF or elevated CPK [43]. Some of these toxicities partially overlap with those already registered for palbociclib, such as diarrhea and decreased blood counts. So we propose to start on 45 mg/BID (binimatinib, continuous dosage) plus 100 mg daily (palbociclib, days 1-21/28). If tolerance is good (no side effects or at most tolerable grade 1 side effects) after a full cycle (28 days) patients will be allowed to escalate palbociclib to 125, according to the study investigators' decision. Alternatively, patients with non-tolerable grade 2 events will resume at 30 mg/BID of binimatinib upon recovery, maintaining palbociclib at 100 mg 21-on/7-off. Depending on the side-effects, in case of clear relationship with palbociclib is established, palbociclib - instead of binimatinib – will be reduced to 75 mg daily.

We propose a single-arm pilot trial testing palbociclib + binimatinib (CDK4/6 plus MEK inhibition) in advanced TNBC to evaluate preliminary activity of this combination by measuring 3-months PFS.

### **5.3. Study objectives**

#### Primary objective:

Primary objective of this study is to determine the 3-months PFS of palbociclib plus binimatinib in advanced triple negative breast cancer (TNBC), in patients with activation of ERK and/or CDK4/6.

### Secondary objectives:

- To determine response rate of the combination in advanced TNBC, in patients with activation of ERK and/or CDK4/6.
- CCI  
[REDACTED]
- To assess the safety of the combination in patients with advanced TNBC.

### Exploratory objective:

[figure not shown]
- CCI

## 6. STUDY DESIGN

## 6.1. Overall design

This is an interventional, prospective, multicentric, single-arm, open label, phase IB clinical trial.

The following scheme depicts the basic trial design.

Patients diagnosed of metastatic or locally advanced non-curable TNBC that have received at least one treatment regimen for advanced disease will be candidates for the trial. A fresh tumor sample will be obtained in order to determine the phosphoproteomic profile of the tumor preferably obtained after last treatment or the most recent sample as possible (from metastatic site or first diagnosis according to sample availability) prior to study inclusion. If the patient has not a tumor sample available prior to study inclusion, the patient will not be allowed to participate in the study. Activation of the two kinases of interest will be determined centrally at CNIO. Only patients with scores above the upper quartile of at least one of them will be candidates (according to our series, approximately 40% of the patients are positive for CDK4/6 and/or ERK).

Patients will then start treatment with continuous oral binimetinib 45 mg/BID and palbociclib 100 mg daily, 21 days on / 7days off, until disease progression. Tumor evaluation will be performed every 8 weeks. Study treatment will continue until disease progression, unacceptable toxicity, intercurrent serious disease, consent withdrawal or investigator's decision.

If treatment tolerance is good (no side effects or at most tolerable grade 1 side effects) after a full cycle (28 days) patients will be allowed to escalate palbociclib to 125, according to the study investigators' decision. Alternatively, patients with non- tolerable grade 2 events will resume at 30 mg/BID of binimetinib upon recovery, maintaining palbociclib at 100 mg 21-on/7-off. Depending on the side-effects, in case of clear relationship with palbociclib is established, palbociclib -instead of binimetinib – will be reduced to 75 mg daily.

The study will be conducted at 8 Spanish sites and will enroll 25 patients.

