### 9.3.2. Binimetinib

For patients receiving 45 mg binimetinib twice daily, the recommended reduced dose of binimetinib is 30 mg twice daily. Dose reduction below 30 mg twice daily is not recommended. Therapy should be discontinued if the patient is not able to tolerate 30 mg orally twice daily.

If the adverse reaction that resulted in a dose reduction is under effective management, dose re-escalation to 45 mg twice daily may be considered. Dose re- escalation to 45 mg twice daily is not recommended if the dose reduction is due to left ventricular dysfunction or any Grade 4 toxicity.

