### Recommended dose modifications for binimetinib for selected adverse reaction.

Severity of adverse reaction a	Binimetinib
Cutaneous reactions	
• Grade 2	Binimetinib should be maintained. If rash worsens or does not improve within 2 weeks with treatment, binimetinib should be withheld until improved to Grade 0 or 1 and then resumed at the same dose if first occurrence or resumed at a reduced dose if recurrent Grade 2.
• Grade 3	Binimetinib should be withheld until improved to Grade 0 or 1 and resumed at the same dose if first occurrence or resumed at a reduced dose if recurrent Grade 3.
• Grade 4	Binimetinib should be permanently discontinued.
Ocular events	
• Symptomatic retinal pigment epithelial detachments (RPED) (Grade 2 or 3)	Binimetinib should be withheld for up to 2 weeks and ophthalmic monitoring should be repeated including visual acuity assessment. 

• If improved to Grade 0 or 1, binimetinib should be resumed at same dose.

• If improved to Grade 2, binimetinib should be resumed at a lower dose.

• If not improved to Grade 2, binimetinib should be permanently discontinued.

• Symptomatic RPED (Grade 4) associated with reduced visual acuity (Grade 4)	Binimetinib should be permanently discontinued.
• Retinal vein occlusion (RVO)	Binimetinib should be permanently discontinued.

Severity of adverse reaction a	Binimetinib
Cardiac events	

 
Grade 2 Left ventricular ejection fraction (LVEF) decrease or asymptomatic, absolute decrease in LVEF of greater than 10 % from baseline that is below lower limit of normal (LLN)
 
	
LVEF should be evaluated every 2 weeks.
 
 
If asymptomatic: Binimetinib should be withheld for up to 4 weeks. Binimetinib should be resumed at a reduced dose if all of the following are present within 4 weeks: 
 
LVEF is at or above the LLN
 
Absolute decrease from baseline is 10 % or less.
 
 
 
If the LVEF does not recover within 4 weeks, binimetinib should be permanently discontinued.
 

 
Grade 3 or 4 LVEF decrease or symptomatic left ventricular dysfunction (LVD)
 
	
Binimetinib should be permanently discontinued. LVEF should be evaluated every 2 weeks until recovery.

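### For a first Grade 2 rash that is non-tolerable and leads to withholding, Protocol 5.2 and 6.1 give one binimetinib resumption dose, the 9.3.2 table gives another, and no text says which governs

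*Protocol*

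**What the plan says.** **Starting dose.** Protocol 6.1: "Patients will then start treatment with continuous oral binimetinib 45 mg/BID and palbociclib 100 mg daily".

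**General rule on Grade 2 events.** Section 5.2 (Summary and considerations) states that "patients with non-tolerable grade 2 events will resume at 30 mg/BID of" binimetinib once they recover. Section 6.1 repeats it; after the prefix non-, its words are "tolerable grade 2 events will resume at 30 mg/BID of binimetinib upon recovery". Both sections then give one exception: "in case of clear relationship with palbociclib is established", palbociclib is reduced instead of binimetinib. Neither section mentions rash, Grade 3 events or the 9.3.2 tables.

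**Rule for rash.** Section 9.3.2 has a table for selected adverse reactions, with separate cutaneous rows. At Grade 2, binimetinib is continued. If the rash worsens, or does not improve within 2 weeks of treatment, it is withheld until Grade 0 or 1 and then "resumed at the same dose if first occurrence or resumed at a reduced dose if recurrent Grade 2". At Grade 3 it is withheld at once until Grade 0 or 1 and then "resumed at the same dose if first occurrence or resumed at a reduced dose if recurrent Grade 3".

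**Related text.** Section 9.3.2 also says that "the recommended reduced dose of binimetinib is 30 mg twice daily". Its second table, for other adverse reactions, withholds binimetinib for recurrent or intolerable Grade 2 reactions and resumes it at a reduced dose after improvement. Section 9.1.1.4 makes reduction optional, according to tolerance and the investigator's criteria.

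**The concern.** A site treating a first Grade 2 rash that the patient cannot tolerate, and that has led to withholding, finds two instructions. Sections 5.2 and 6.1 restart binimetinib at the reduced dose; the cutaneous row restarts it at the same dose. It cannot follow both, and the protocol does not rank them.

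The stakes are in the exposure data. SAP 7.2 tabulates dose reductions with reasons for each drug. SAP 7.3 describes relative dose intensity against the theoretical dose the patient should have received under the protocol. With 25 patients at 8 sites, a few decisions taken from different sections could be visible in these tables, and a reduction could then reflect the section a site consulted as well as tolerability. Safety of the combination is a secondary objective, so these tables matter.

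**Working it through.** The plan states no figure to reproduce. The check compares the texts and adds a little arithmetic.

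**1. The rules side by side** (patient on 45 mg BID, first rash, not clearly related to palbociclib)

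| Event | 5.2 and 6.1 | 9.3.2, cutaneous rows |
|---|---|---|
| Grade 2, non-tolerable | resume at 30 mg BID | tolerability not mentioned |
| Grade 2, worsens or no improvement within 2 weeks | course not mentioned | withhold, resume at the same dose (45 mg BID) |
| Grade 2, both of the above | 30 mg BID | 45 mg BID |
| Grade 3 | silent | withhold, resume at the same dose (45 mg BID) |

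The triggers are not the same, but a Grade 2 rash that worsens under treatment can also be non-tolerable. The third row is the contradiction.

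**2. Size of the dose difference**

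- 6.1: 2 × 30 = 60 mg/day. 9.3.2: 2 × 45 = 90 mg/day.
- Difference: (90 − 60)/90 = 33%.
- In the SAP's unit of mg/week: 7 × 60 = 420 against 7 × 90 = 630.

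**3. Consequence for relative dose intensity.** Assume that the SAP's denominator follows the patient-level dose rules, which SAP 7.3 does not spell out, and count only weeks after resumption with no missed doses. A patient resumed at 30 mg BID then has 420/420 = 100% if 6.1 is the protocol dose and 420/630 = 67% if 9.3.2 is. If the denominator is simply the starting dose, the value is 67% under either text and the ambiguity affects only the dose actually given.

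**4. How far the conflict extends**

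- The selected-reaction table has the same-dose pattern in two other places: symptomatic Grade 2 or 3 retinal pigment epithelial detachment that improves to Grade 0 or 1, and Grade 2 AST or ALT elevation withheld after no improvement within 2 weeks.
- For reactions without their own row, the second 9.3.2 table reduces the dose for intolerable Grade 2 events, in agreement with 6.1.

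**5. How many patients could have a rash at all**

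Any-grade rates in the single-agent studies, Protocol 5.1.3.5.1:

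| Study | Rash | Acneiform dermatitis |
|---|---|---|
| ARRAY-162-111 | 59% | not in the common-event list |
| CMEK162X1101 | 38.1% | 47.6% |
| CMEK162X2201, 60 mg BID | 20.0% | 32.0% |
| CMEK162AUS11 | 43.6% | not in the common-event list |
| CINC280X2205 | 72.7% | not in the common-event list |
| ARRAY-162-311 | not in the common-event list | 49% |

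For rash the range is 20.0% to 72.7%: 25 × 0.200 = 5.0 and 25 × 0.727 = 18.2, so about 5 to 18 of 25 patients. No combined rate for the two terms is given. Nor is the share that is first-occurrence Grade 2, non-tolerable and withheld, so the number of patients in conflict cannot be derived.

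**The case against.** The best reply is that 6.1 is an overview and 9.3, the section on dose adjustment, holds the detail, so a specific row overrides a general sentence. That reading is plausible, and the agreement between 6.1 and the second 9.3.2 table supports it. But the protocol does not state it, and the wording does not settle it: 6.1 uses *will*, the table is headed as recommended and uses *should*, and 9.1.1.4 uses *may*. Nor is 9.3 plainly adapted to this trial: 9.3.1 lists palbociclib 125 mg as the recommended dose and 100 mg as the first reduction, while 6.1 starts patients at 100 mg.

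Two further replies stand in part. The triggers differ, so not every Grade 2 rash is in conflict. Re-escalation is allowed under 9.1.1.4 and 9.3.2, so a reduction need not last.

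A reader might infer more than the documents support:

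- *That the plan reduces Grade 2 rash and spares Grade 3.* Neither text does so alone. The ordering appears only if 6.1 is applied to Grade 2 and 9.3.2 to Grade 3. Nothing forbids that combination, but nothing prescribes it.
- *That 5.2 and 6.1 allow no exception.* They allow one, for events clearly related to palbociclib.
- *That the conflict will arise often.* The rash rates are for any grade, and the relevant share is not given. On the Grade 3 side, ARRAY-162-111 reports Grade 3 rash and Grade 3 acneiform dermatitis in 2 of 93 patients each (25 × 2/93 = 0.5 per term). Neither term appears among the severe events listed above the reporting thresholds in the other five studies described.
- *That 3-month PFS will be distorted.* Dose intensity is descriptive, no planned analysis links exposure to PFS, and investigator discretion under 9.1.1.4 already lets dosing vary.

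**Conclusion.** Wrong as written: an internal contradiction in the dosing instructions. For a first Grade 2 rash that is non-tolerable, leads to withholding and is not clearly related to palbociclib, the protocol gives 60 mg/day in one place and 90 mg/day in another, a difference of one third, and does not say which applies.

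The conclusion rests on the two triggers overlapping in some patients and on the absence of a precedence statement. It does not rest on any rash rate. The contradiction is limited to reactions with their own rows in 9.3.2. Its frequency is unknown, and its effect on dose reductions and relative dose intensity is possible but unquantified. No view is taken on which rule is right.

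**What to change.** Reconcile Protocol 5.2, 6.1, 9.1.1.4 and both binimetinib tables in 9.3.2. Add one sentence, in 6.1 and in 9.3.2, stating which text governs Grade 2 events that have their own row in the selected-reaction table. The statement should cover the retinal and AST/ALT rows as well as rash. The sponsor's clinicians choose the rule.

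Notify sites once it is settled. The cost is one governing sentence with matching edits in the protocol, and a note to sites.

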### **Study of immune resistance to study drugs**

In addition to evaluate the efficacy of study treatment, it is highly probable that in the long term the tumor will grow again, even if promising data on activity are found. It is necessary to investigate the reasons that lead to this event, in order to be able to design new therapies or therapeutic combinations that delay or prevent the development of resistance.

To do this, we are working with murine models of breast cancer that mimic the therapeutic scenario of advanced breast cancer, but it is necessary to study and validate the possible findings in the clinical setting.

Currently, we are trying to understand how different targeted therapies impact the immune system's ability to control tumor growth. **CCI**

Redacted content block consisting of 10 horizontal black bars of varying lengths, with a larger bar at the bottom.

## 6.2. Primary endpoint

- Three-months PFS.

## 6.3. Secondary endpoints

- Overall response rate.
- CCI [REDACTED]
- Number of patients experiencing each AE will be summarized by CTCAE grade to evaluate safety profile, according to NCI-CTC v 5 criteria.

## 6.4. Exploratory endpoints:

- CCI [REDACTED]  
[REDACTED]  
[REDACTED]

# 7. PATIENT SELECTION

## 7.1. Inclusion criteria

Patients must meet the following criteria for study entry:

1. Women >18 years-old.
2. Diagnostic of metastatic or locally advanced non-resectable TNBC.
3. Patient must have received a minimum of one and a maximum of two treatment lines for metastatic TNBC. Previous treatments can be of any nature (chemotherapy, immunotherapy, antiangiogenics, experimental therapy, etc.).

Women with known BRCA1/BRCA2 germline mutations must have received a platinum based treatment or treatment with a PARP inhibitor.

4. Patient must have experienced disease progression to the previous treatment line according to the RECIST 1.1 or iRECIST criteria.
5. Availability of tumor tissue for ERK and CDK4/6 testing is mandatory prior to study inclusion, preferably obtained after last treatment or the most recent sample as possible (from metastatic site or first diagnosis according to sample

availability). If the patient has not a tumor sample available prior to study inclusion, the patient will not be allowed to participate in the study.

6. Ability to understand and signing of the written patient information/informed consent form (PIS/ICF) for ERK and CDK4/6 testing. ERK and CDK4/6 testing will be performed centrally at CNIO.
7. Ability to understand and signing the written PIS/ICF for study treatment eligibility. Signed informed consent form must be available before any study- specific procedure for the respective study parts may begin.
8. Positivity for ERK and/or CDK4/6, defined as showing an H-score above the top-quartile according to published definitions [1].
9. ECOG performance status of 0-1.
10. Evaluable disease according to RECIST 1.1 criteria.
11. Life expectancy >24 weeks.
12. Adequate bone marrow, liver and renal function as assessed by laboratory requirements conducted within 7 days before first study drug administration:
  - a. Absolute neutrophil count (ANC)  $\geq 1.500/\text{mm}^3$  (without granulocyte colony-stimulating factor support within 2 weeks before the first study drug administration)
  - b. Hemoglobin  $\geq 9 \text{ g/dL}$  (without transfusion or erythropoietin within 4 weeks before the first study drug administration)
  - c. Platelet count  $\geq 100.000/\text{mm}^3$  (without transfusion within 2 weeks before the first study drug administration)
  - d. Total bilirubin  $\leq 2 \times$  the upper limit of normal (ULN).
  - e. Alanine aminotransferase (ALT) and aspartate aminotransferase (AST)  $\leq 2.5 \times$  ULN ( $\leq 5$  times ULN for patients with liver metastases)
  - f. Glomerular filtration rate (GFR)  $> 50 \text{ mL/min}/1.73 \text{ m}^2$  according to the modification of diet in renal disease (MDRD) abbreviated formula.

13. Patients must have recovered to  $\leq$  Grade 1 in terms of toxicity from prior treatments (excluding neuropathy which can be  $\leq$  Grade 2, and alopecia).
14. Patients must be able to take oral medications.
15. Patients must have adequate cardiac function, defined as:
  - a. Left ventricular ejection fraction (LVEF)  $> 50\%$  as determined by echocardiogram or multigated acquisition scan (MUGA).
  - b. QTc  $< 480$  msec.
16. Negative serum pregnancy test in women of childbearing potential (performed within 7 days before the first treatment). Negative results must be available before the first study drug administration.

A postmenopausal state is defined as no menses for 12 months without an alternative medical cause. A high follicle stimulating hormone (FSH) level in the postmenopausal range may be used to confirm a post-menopausal state in women not using hormonal contraception or hormonal replacement therapy. However in the absence of 12 months of amenorrhea, a single FSH measurement is insufficient.

Pregnancy test will not be performed in postmenopausal women.

17. Women of reproductive potential must agree to use adequate contraception when sexually active. This applies for the time period since the signature of the informed consent form and until at least 1 month after the last study drug administration. The definition of adequate contraception will be based on the judgment of the investigator and on local requirements. Acceptable methods of contraception include, but are not limited to, (i) condoms (male or female) with or without a spermicidal agent; (ii) diaphragm or cervical cap with spermicide; (iii) intra-uterine device; (iv) hormone-based contraception.

Zoledronic acid or denosumab started prior to trial registration is allowed, but in case they are required after initiation of trial procedures, adequate justification is required.

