#### **5.1.3.6. Guidance for Investigators**

Binimatinib is an investigational drug for which limited safety data are available. It should be used with appropriate caution typical for an investigational drug.

Binimetinib has demonstrated an acceptable and manageable safety profile in nonclinical toxicology studies and clinical studies. As with any investigational drug, unexpected AEs may occur.

Available clinical data for binimetinib indicate a predictable safety profile consistent with those reported for other allosteric MEK1/2 inhibitors including the characteristic class effects of ocular toxicities, elevations of CK that are mostly asymptomatic, liver function test abnormalities (elevation of aspartate aminotransferase [AST], alanine aminotransferase [ALT] and total bilirubin), left ventricular dysfunction, skin toxicities including rash and acneiform dermatitis, hypertension, thromboembolic events, diarrhea, edema and hemorrhage. The majority of these toxicities are generally reversible and manageable by appropriate supportive medical care and/or dose modifications or discontinuation. Supportive therapy for the management of binimetinib-associated toxicities should be based on Investigator experience.

Binimetinib may cause fetal harm (teratogenicity) when administered to a pregnant woman. Binimetinib must not be used in pregnant women or nursing women, and the use of highly-effective contraception is recommended for male and female subjects participating in clinical studies. Additionally, women of childbearing potential must be advised to use highly effective contraception.

Ocular toxicities can occur with binimetinib administration. Patients should be assessed for symptoms of new or worsening visual impairment. Patients with a history or current evidence of retinal vein occlusion (RVO) or risk factors for RVO (e.g., uncontrolled glaucoma or history of hyperviscosity or hypercoagulability syndrome) should be excluded from studies with binimetinib.

New onset hypertension, or worsening of pre-existing hypertension, can occur with the use of binimetinib. Patients should be monitored for hypertension and treated as needed with standard anti-hypertensive therapy.

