Left ventricular dysfunction, defined as symptomatic or asymptomatic decreases in ejection fraction, can occur with binimetinib. Before binimetinib administration, patients should have a baseline left ventricular ejection fraction (LVEF) evaluation and periodically on study as per protocol.

Venous thromboembolism can occur with the use of binimetinib. Binimetinib should be used with caution in patients who are at risk for, or who have a history of venous thromboembolism.

Rash events are among the most frequently observed AEs reported with MEK inhibitors when used as a single agent. Patients receiving binimetinib should be monitored for skin toxicities and for secondary infections.

Overall, the risk for binimetinib to be a cause of or be affected by significant drug- drug interactions is predicted to be low. However, given the predominant role of

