12. Malabsorption syndrome or uncontrolled nausea, vomiting, or diarrhea that may interfere with the absorption of oral study medication in the opinion of the investigator.

13. Pregnant women or breast-feeding.

14. Known HIV-positive individuals on combination antiretroviral therapy.

15. Active hepatitis B virus (HBV; chronic or acute; defined as having a known positive hepatitis B surface antigen [HBsAg] test at the time of screening) or hepatitis C infection requiring treatment.

- a. Patients with past HBV infection or resolved HBV infection (defined as the presence of hepatitis B core antibody [HBcAb] and absence of HBsAg) are eligible if HBV DNA is negative.

- b. Patients positive for hepatitis C virus (HCV) antibody are eligible only if polymerase chain reaction is negative for HCV RNA.
- 16. Any condition that in the opinion of the investigator would interfere with evaluation of study treatment or interpretation of patient safety or study results, or inability to comply with the study and follow-up procedures.
- 17. Participation in another clinical study with investigational medicinal products within 4 weeks before the first study drug administration.
- 18. Clinically active infections within 2 weeks before the first study drug administration.
- 19. Treatment with therapeutic oral or i.v. antibiotics within 2 weeks before the first study drug administration. Patients receiving prophylactic antibiotics (e.g. for prevention of a urinary tract infection or to prevent chronic obstructive pulmonary disease exacerbation) are eligible.
- 20. Known hypersensitivity to any of the study drugs, study drug classes, or excipients in the formulation.
- 21. Current diagnosis of any retinal disorders including retinal detachment, retinal pigment epithelial detachment (RPED), serous retinopathy or retinal vein occlusion or risk factors for RVO (e.g., uncontrolled glaucoma or history of hyperviscosity or hypercoagulability syndrome).
- 22. Peripheral sensory neuropathy of CTCAE v.5.0 Grade 2 or higher
- 23. Major surgery, open biopsy or significant traumatic injury within 4 weeks before the first study drug administration (central line surgery is not considered major surgery).
- 24. Renal failure requiring peritoneal dialysis or hemodialysis.
- 25. Substance abuse, medical, psychological or social conditions that may interfere with the patient's participation in the study or evaluation of the study results.

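### Inclusion criterion 17 asks only for adequate contraception and does not tie eligibility to the highly effective standard that section 5.1.3.6 recommends for binimetinib

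*Protocol*

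**What the plan says.** Criterion 17 appears in protocol 1.13.1, protocol 7.1 and SAP 3.8. It obliges women of reproductive potential to agree to adequate contraception when sexually active, from signing consent until at least 1 month after the last dose. On what counts as adequate it says: "The definition of adequate contraception will be based on the judgment of the investigator and on local requirements". It then names methods as acceptable without closing the list. Those named are condoms (spermicide optional), diaphragm or cap with spermicide, intra-uterine device, and hormonal contraception.

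Protocol 5.1.3.6 gives drug-specific guidance. It states the hazard: "Binimetinib may cause fetal harm (teratogenicity) when administered to a pregnant woman". It states the standard: "the use of highly-effective contraception is recommended for male and female subjects participating in clinical studies". It then places a duty on the site: "Additionally, women of childbearing potential must be advised to use highly effective contraception".

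Criterion 17 does not refer to section 5.1.3.6, and no other entry criterion requires highly effective contraception.

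**The concern.** The protocol names a contraception standard for this drug because of possible fetal harm, and then checks eligibility against a different and looser term. Section 5.1.3.6 governs what the site must tell the woman. Criterion 17 governs what she must agree to in order to enter. Only the second is verified at enrolment, and it contains no effectiveness threshold.

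What is at stake is fetal exposure to a drug that the protocol describes as potentially teratogenic. The harm would be serious if it occurred. The trial's efficacy and safety estimates are not at stake.

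**Working it through.** The plan gives no figure to reproduce and no formula applies. The check is a comparison of texts, followed by a test of whether another safeguard closes the gap.

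**Step 1: compare the two standards.**
- Level. Criterion 17 says adequate; section 5.1.3.6 says highly effective.
- Who decides. Under criterion 17, the investigator together with local requirements. Section 5.1.3.6 names the standard but does not define it.
- Methods. Criterion 17 has an open list; section 5.1.3.6 has none.
- Force. Criterion 17 is a condition of entry. Section 5.1.3.6 is a recommendation plus a mandatory duty to advise.

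**Step 2: can both be met at once?** Yes. A site can give the advice and an investigator can use section 5.1.3.6 when judging adequacy. Protocol 14.1 requires the trial to follow the protocol, so the duty to advise is binding.

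**Step 3: can criterion 17 be met without the higher standard being applied?** Also yes. Suppose a woman receives the advice, opts for one of the named methods, and agrees to use it throughout. Criterion 17 is satisfied, and nothing in it requires anyone to ask whether the method is highly effective.

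**Step 4: do the other safeguards close the gap?**
- The negative serum test before the first dose (inclusion 16) and the exclusion of pregnant women (exclusion 13) protect a pregnancy that already exists at entry.
- Tests on day 1 of each cycle (10.2), at end of treatment (10.3) and at safety follow-up (10.4) detect a new pregnancy. Binimetinib is taken continuously and on-treatment tests are 4 weeks apart, so exposure before detection could be of the order of one test interval.
- Pregnancy reporting within 24 hours (11.3.7) follows the event.
- The duty to advise is preventive, but it does not bind the woman's choice.

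None of these sets a threshold for the method used.

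**Step 5: size.** The number affected would be the 25 planned patients (6.1) multiplied by three shares: of childbearing potential, sexually active, and using a method below the higher standard despite advice. The documents give none of the three. The product can therefore be anything from 0 to 25, which is the whole sample and carries no information.

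**The case against.** The best defence is that nothing is broken. The texts are compatible, the advice is mandatory, and criterion 17 rests on local requirements as well as investigator judgment, so discretion is not unlimited. All 8 sites are in Spain and work under the same national decree and EU regulation (14.1). On this view the point is a preference for stricter wording. Much of that stands, and it limits what can be claimed. It does not answer step 3: compatibility still leaves eligibility untied to the standard that the protocol names.

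A reader might infer stronger things that the documents do not support:
- *That the two sections contradict each other.* They do not; both can be followed.
- *That particular listed methods fall short.* The documents neither define highly effective nor rank methods. The supportable statement is that the method need not be checked against the standard, not that it fails it.
- *That the required level differs between sites.* This is possible, but not shown. What local requirements demand is not in the documents.
- *That the omission is an evident slip, because neighbouring guidance became entry criteria.* The pattern is only suggestive. The retinal vein occlusion guidance itself asks for exclusion ("or risk factors for RVO (e.g., uncontrolled glaucoma or history of hyperviscosity or hypercoagulability syndrome) should be excluded from studies with binimetinib"), so exclusion 21 follows directly ("serous retinopathy or retinal vein occlusion or risk factors for RVO"). The cardiac guidance asks for an evaluation ("Before binimetinib administration, patients should have a baseline left ventricular ejection fraction (LVEF) evaluation and periodically on study as per protocol"), while inclusion 15 ("Patients must have adequate cardiac function, defined as") adds an LVEF threshold that this guidance does not state. Contraception is worded as a recommendation and a duty to advise. Other cautions in 5.1.3.6, such as that on a history of venous thromboembolism, did not become general entry criteria either.
- *That the advice is missing from the consent form.* The form was not available for review, so nothing can be said about it.

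**Conclusion.** The point holds as a limited patient-safety improvement that should be made. Criterion 17 is a stated entry rule with no effectiveness threshold. A site that follows it exactly can enrol a woman whose method was never assessed against the protocol's own standard for binimetinib. The existing safeguards are real but do not supply that threshold.

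The conclusion rests on the text of criterion 17 and section 5.1.3.6, and on the absence of any other entry criterion that sets the higher standard. It assumes nothing about how sites would exercise judgment, what local requirements say, or what the consent form contains. How many women would be affected cannot be estimated. No endpoint, analysis population or statistical result changes.

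**What to change.** Amend criterion 17 in protocol 1.13.1, protocol 7.1 and SAP 3.8:
- Reword the requirement to: *Women of childbearing potential must agree to use highly effective contraception when sexually active.*
- Keep the period as it stands.
- Replace the sentence on investigator judgment and the open list with a closed list, supplied by the sponsor, of methods that meet the standard. The list is essential, because the documents do not define the term and rewording alone would swap one undefined word for another.
- State that stricter local requirements continue to apply.
- Check that the consent form uses the same standard and list.

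The cost is a wording amendment in three places, the sponsor's list, and the consent-form check. Entry becomes slightly stricter for sexually active women of childbearing potential. Women who are not sexually active are unaffected, and the statistical analysis needs no change.
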